E-cigarettes are popular; in England use by smokers and recent ex-smokers currently stands at around 20% and around 30% used e-cigarettes in quit attempts in 2021, compared with 3% of smokers accessing SSS [31]. E-cigarette use is increasingly being recorded by SSS [32], and appeal in particular to PWMI who are more likely to have tried e-cigarettes and be current users than smokers in the general population [33]. There are several reasons for this. Firstly, e-cigarettes are relatively cheap compared with both cigarettes and other cessation treatment [34]. Second, they offer a simple stand-alone treatment that is intuitive to use. Third, since e-cigarettes simulate the sensory input from cigarettes and allow users to control the dose (unlike most NRT), they may appeal to more dependent smokers who have hitherto struggled to quit, with the potential to enhance existing cessation treatments and replace combustible tobacco products [35]. Thus e-cigarettes may be one solution to reduce smoking and encourage cessation in mental health care settings by functioning as a safer alternative to cigarettes [36].

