3.2 Study objectives

- 3.2.1 Primary research objective: to assess the feasibility and acceptability of the ecigarette-based intervention and associated research processes in our study population, establishing central parameters for the design of a definitive RCT (Phase II), including recruitment and retention rates.
- 3.2.2 Secondary research objectives: (1) to determine whether progression to a full trial is reasonable, based on the confidence interval approach [47] (see also 1.9); (2) to establish e-cigarette adherence rates and potential level of contamination between study arms to inform planning for a full trial; (3) to assess fidelity of intervention delivery; (4) to establish the feasibility of data collection and training procedures and pilot the gathering of cost data to inform methods for health economic analysis in Phase II; (5) to explore barriers and facilitators to participation; (6) if indicated, to refine the intervention and study protocol in readiness for a full RCT.

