3.8.3.1 Feasibility and acceptability outcomes: Fidelity will be assessed by randomly sampling two intervention sessions per site with trained staff, audio-recording them and coding the use of behaviour change techniques (BCTs) delivered during the session to determine the proportion of BCTs used compared to specification in the manual [66]. Characteristics of 'usual care' in different locations will be also noted, recording two interactions of patients with CMHTs or GPs at each site at baseline and using short proforma with control group participants at follow-up. While the nature of the intervention and delivery format means that contamination is unlikely to be a problem, qualitative exploration will be undertaken with 25% of control group patients to investigate in depth reasons for smoking behaviour change and identifying potential (unintentional) links with our intervention. Based on our findings, we will estimate the presence/extent of contamination in the control group, and the need to change the study procedure (e.g. spacing randomisation per site). Further, the feasibility of intervention delivery via CPNs and using both English and Urdu will be assessed by calculating the number of successfully trained CPNs in each Trust, their recruitment rate and fidelity of intervention delivery as well as the proportion of Urdu speakers successfully recruited into the trial. Participant burden of data collection will be asssessed via qualitative interviews conduction online or via telephone with particpants to assess acceptability, which forms part of our list of measures collected in the feasibility study (Phase 1) to determine stop/go decision for the Phase 2 full trial. Should this issue be raised as a barrier to participation, we will seek to prioritise which measures to retain in the full trial.

3.8.3.2 Clinical (smoking-related) outcomes: Self-reported abstinence 2-4 weeks from enrolment or target quit date (whichever is later) will be recorded at 1-month follow-up. The change in cigarette consumption (and reduction in exhaled breath CO reading) from baseline to 1-month follow-up will be calculated in both intervention and control group participants.

3.8.3.3 Clinical (mental health-related) outcomes: At 1-month follow-up, general and mental health functioning will be assessed as per baseline (see 3.8.1.3).

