4.5.2 Secondary outcome measures

- 4.5.2.1 Clinical (smoking-related) outcomes: At one month, self-reported and CO-verified smoking abstinence rates, 2-4 weeks from enrolment or target quit date (whichever is later) will be recorded. Continuous abstinence at 6-month follow-up will be defined as not having had more than 5 cigarettes between two weeks after enrolment and follow-up, in line with Russell standards [77]. Unsuccessful quit attempts in the past six months will also be recorded. In line with the feasibility trial, smoking reduction in cigarette consumption by 50% or in CO reading by 30% will be assessed at both 1- and 6-month follow-up.
- 4.5.2.2 Clinical (mental health-related) outcomes: At 6-month follow-up only, general and mental health functioning will be assessed using measures detailed in 3.8.1.3.
- 4.5.2.3 Practical (design-related) outcomes: As in Phase I, attrition and, in the intervention group, adherence rate will be assessed at 1-month follow-up. Attrition will also be assessed at 6-months follow-up, in addition to continued use of e-cigarettes in the intervention group and de novo e-cigarettes use in the control group.
- 4.5.2.4 Psychosocial outcomes: Health-related quality of life will be assessed using EQ-5D-5L [82] and the mental health specific ReQoL [83] at final follow-up. Health and social care service use will be measured using the Client Service Receipt Inventory (CSRI), which has been validated against objective primary care records [84] and is also recommended for usage of hospital and other community health services [85]. Changes from baseline in other health behaviours (see 3.8.1.4) will be determined at 6-month follow-up.
- 4.5.2.5 Cost effectiveness: To determine short-term cost-effectiveness of the intervention, we will undertake a within-trial incremental cost-effectiveness analysis to assess the value

for money afforded by the intervention over and above the usual care using data collected during the trial. A service use questionnaire piloted in the feasibility workstream will be used to collect resource use at baseline, one and six months and will include both the cost of providing the interventions and the costs of patients' health care utilisation from an NHS perspective as recommended by NICE technology appraisal guide [86]. To assess long-term cost, effectiveness, we will undertake economic modelling (see 4.7).

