4.6 Power Calculation

The full trial will be powered to detect a difference between the intervention and control group in our primary outcome: 6-month abstinence rate (see 4.5). Pooling results of the only three RCTs comparing e-cigarettes with placebo e-cigarettes [38, 39, 87] yields an expected effect size of OR 2.01 for 6-months abstinence rates. We consider this estimate to be conservative as most of these trials used older, less effective first-generation ecigarettes. In fact, a recently published trial comparing an active treatment (NRT) with a modern, third generation e-cigarette in the context of stop smoking services [41] found a superior effect of e-cigarettes on 6-months abstinence rates of OR 1.63. Based on established effect estimates for NRT vs placebo [88], findings from this trial therefore indirectly suggest that compared with placebo/usual care, third generation e-cigarettes (as will be used in this trial) may increase 6-months abstinence rates nearly three-fold (OR 2.85). Using the more conservative effect estimate of OR 2.01, we expect an absolute predicted risk difference of 6.7%, assuming 6-months abstinence rates in the control (standard care) group of 7.7% (based on EAGLES [67] and SCIMITAR-plus [30] trials which were conducted in PWMI) and 14.4% in the intervention (e-cigarette) group. A sample of 740 participants (370 per group) would provide 80% power, with alpha=0.05 in two-tailed analysis to detect this conservative effect. This sample size would also provide 95% power to detect a more likely effect of OR 2.43 (intermediary between the conservative and more optimistic effect), with an absolute predicted risk difference of 9.2% at 6 months (7.7% for control group vs 16.9% for treatment group).

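### Phase I is meant to establish the level of contamination but names only nine control interviews to do so, and section 4.6 states no allowance for e-cigarette use among controls

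*Protocol*

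**What the plan says.** Among the Phase I secondary objectives, Protocol section 3.2.2 lists: "to establish e-cigarette adherence rates and potential level of contamination between study arms to inform planning for a full trial". Section 3.8.3.1 gives the method. It judges that "contamination is unlikely to be a problem, qualitative exploration will be undertaken with 25% of control group patients". The interviews are to explore why controls changed their smoking and whether there were unintended links with the trial intervention. From them the team will estimate whether contamination is present and how far it extends. The example given of a change in procedure is to space randomisation within sites.

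On measuring use at 1 month, section 4.5.2.3 says: "As in Phase I, attrition and, in the intervention group, adherence rate will be assessed at 1-month follow-up". The same section adds that at 6 months in Phase II, new e-cigarette use in the control group will be recorded. Section 3.8.3.1 also gives control participants a short form at follow-up, described as a record of usual care; e-cigarette use is not mentioned there.

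Section 3.13 promises an updated sample size calculation at the stop/go point. None of its criteria a) to e) concerns contamination. Section 4.6 states: "A sample of 740 participants (370 per group) would provide 80% power, with alpha=0.05 in two-tailed analysis", "assuming 6-months abstinence rates in the control (standard care) group of 7.7"% and "14.4% in the intervention (e-cigarette) group". The effect comes from pooled comparisons with placebo e-cigarettes, which "yields an expected effect size of OR 2.01 for 6-months abstinence rates". No allowance for e-cigarette use among controls is stated.

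The background (section 1) reports that, in England, "around 30% used e-cigarettes in quit attempts in 2021". It adds that people with mental illness are more likely than other smokers to have tried these products and to be using them.

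**The concern.** A level of contamination is a proportion, and a proportion needs a count in a defined group. Qualitative interviews with nine people can explain how and why controls came to use e-cigarettes. They cannot say how many did so with a precision that helps to plan a trial of 740.

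The timing adds to this. The updated sample size is due at the end of Phase I. The one stated measurement of new control use comes at 6 months in Phase II. Section 4.8 starts Phase II recruitment in month 17, so no 6-month data exist before about month 23, well after the stop/go decision.

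Controls are smokers willing to quit or cut down, they know their allocation, and they can buy an e-cigarette in a shop. Whatever its source, effective use by controls narrows the difference between the groups. If the update has no figure for it, the 80% power carries a risk that the plan has not sized.

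**Working it through.** **Inputs.** Phase I has 36 controls (section 3.9), of whom 25% are explored (section 3.8.3.1). Phase II has 370 per group, 7.7% against 14.4%, and two-sided alpha 0.05 (section 4.6). Fisher's exact test is the first primary analysis (section 4.7.1).

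**Step 1: precision in Phase I.** 0.25 × 36 = 9 controls. Exact (Clopper-Pearson) 95% intervals:

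| Users found | Interval |
|---|---|
| 0 of 9 | 0 to 34% |
| 2 of 9 | 3 to 60% |
| 8 of 36 | 10 to 39% |

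For 0 of 9 the upper limit is 1 − 0.025^(1/9) = 0.336. Finding no users among nine would not exclude uptake of 30%.

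**Step 2: reproduce the plan's power.** The exact power of the two-sided Fisher test at 370 per group, 7.7% against 14.4%, is 80.4%. This matches the stated 80%. For the plan's second scenario (OR 2.43, 7.7% against 16.9%) it is 96.4%, against a stated 95%.

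**Step 3: add control uptake.** Let c be the share of all controls who take up e-cigarettes and f the share of the intervention benefit that each of them gains. Then

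control rate = 7.7% + c × f × (14.4% − 7.7%).

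For c = 0.30 and f = 1: 7.7% + 0.30 × 6.7% = 9.71%, so the difference falls from 6.7 to 4.69 points. Fisher power at 370 per group, OR 2.01:

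| Uptake c | Control rate, f = 1 | Power, f = 1 | Control rate, f = 0.5 | Power, f = 0.5 |
|---|---|---|---|---|
| 0 | 7.70% | 80% | 7.70% | 80% |
| 10% | 8.37% | 70% | 8.04% | 75% |
| 20% | 9.04% | 58% | 8.37% | 70% |
| 30% | 9.71% | 46% | 8.71% | 64% |

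**Step 4: the plan's more likely effect.** With 16.9% in the intervention group, c = 0.30 and f = 1, the control rate is 7.7% + 0.30 × 9.2% = 10.46%. Fisher power is then about 69%.

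**Step 5: what the 30% refers to.** It is a share of quit attempts. It equals c only if every control makes an attempt. If half do (an assumption), c = 0.30 × 0.5 = 15%, and power with full benefit under OR 2.01 is 64%.

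**The case against.** The strongest reply is that two things must be kept apart. Section 3.8.3.1 speaks of spill-over from the trial kit, as its reference to links with the intervention shows. The 30% in the background is ordinary use in the population. In a pragmatic comparison with usual care, e-cigarettes that controls buy for themselves can be seen as part of the comparator. A reader might infer that section 1 refutes the statement that contamination is unlikely. It does not, because the two passages describe different routes. Likewise, spacing randomisation cannot be faulted for failing to prevent shop purchases, since it was offered against spill-over. This part of the reply stands. Background use remains a question for the power calculation.

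A reader might also infer that controls are never asked about e-cigarettes at 1 month. The protocol does not say so. It does not list the survey items, and the usual-care form goes to control participants. What can be said is that no such item is named, and that use at 1 month appears only as adherence in the intervention group.

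The plan has further safeguards: smokers who use e-cigarettes at least weekly are excluded at entry (section 3.6.1), Phase II records new control use at 6 months, and the sample size is to be updated. The exclusion does not prevent uptake after randomisation, and the 6-month record helps interpretation but comes too late for the update.

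Finally, 36 controls also give a wide interval. That is true, but 10 to 39% can be carried into a calculation as a range, which nine interviews chosen for depth do not support.

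**Conclusion.** The point holds as a gap between an objective and its method, together with a power statement that shows no sensitivity to control uptake. Nine qualitative interviews cannot establish the level that section 3.2.2 promises, and no other named measure fills the gap before the updated calculation.

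The size depends on assumptions. Under OR 2.01, uptake of 10% would cost about 5 points of power with half benefit and about 10 with full benefit; 20% would cost about 10 and 22. The case for acting does not need the 30% row. A reader might infer that the trial's real power is 46%, but the documents do not support that. The figure applies a share of quit attempts in England to all controls, some of whom only want to cut down, and gives each the full effect of the kit. It is close to a worst case under the effect that the plan itself calls conservative. Half benefit gives 64% at the same uptake, and OR 2.43 with full benefit about 69%.

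All these figures assume that the 7.7% control rate, taken from earlier trials, does not already include such use. The protocol does not say whether it does; if it does, the loss is smaller.

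**What to change.** - Add an e-cigarette item (any use, at least weekly use, source) to the 1-month follow-up survey for every control participant, above all in Phase I. If the survey or the usual-care form already has one, name it in section 3.8.3.1.
- Keep the interviews for reasons and for links with the trial kit.
- In section 3.13, state that the Phase I proportion, with its interval, enters the updated sample size calculation.
- In section 4.6, show power for 740 over a range of control uptake as a labelled sensitivity analysis. Give full and half benefit under OR 2.01, state the assumption about the 7.7%, mark 46% as near the worst case, and add about 69% for OR 2.43 at 30% uptake with full benefit.
- In section 3.8.3.1, the judgement that contamination is unlikely can stay if it is limited to spill-over from the trial kit. Treat background e-cigarette use separately.

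The cost is one short item in a survey that is already administered, a few sentences of text, and a less favourable power range. Treatment and the primary outcome do not change.

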3.9 Power Calculation

The target sample size for the randomised controlled feasibility trial will be 72, with 36 participants allocated to each group. In a full RCT, we would assume an effect size of OR (odds ratio) of 3.9 (pooled estimate based on e-cigarette vs placebo e-cigarette trials: [38, 39]) for the primary clinical outcome (1-month continuous abstinence rate). This would result in an absolute predicted risk difference of 8.2%, assuming a 1-month abstinence rate in the control (usual care) group of 11.4% [based on EAGLES trial [67]] and 19.6% in the intervention (e-cigarette starter kit and usual care) group. The pilot sample size would be sufficient to produce a one-sided confidence interval that excludes an 8% difference in the event of a zero effect of the intervention on abstinence at 1 month, assuming 11% reported abstinence in each of the two groups. The estimate obtained in the feasibility trial will not be used to directly estimate the intervention effect (see 2.5) but to determine whether proceeding to a trial is worthwhile, based on the confidence interval approach [47].

In addition, the Phase I study is powered to detect clinically relevant within-subject changes in two secondary clinical outcome measures: cigarette and exhaled breath CO reductions. A recent study [8] in which smokers with mental illness, who were not intending to quit smoking, were provided with e-cigarettes showed that half of smokers

reduced their cigarette consumption by 50%. This e-cigarette supported level of reduction has been linked to a significant lowering in exposure to biomarkers of smoking-related harm [68]. Further, such smoking reduction in concert with provision of non-combustible nicotine delivery devices may aid future complete cessation [69]. The target outcome is therefore a reduction in cigarette consumption by at least 50% (or a 30% reduction in CO levels, common for smoking reduction of this magnitude [70]). Half the sample size in the intervention group (those expected to reduce consumption, n=18) provides 80% power to detect a medium- to large-sized effect (Cohen's d=0.7), reflecting a 50% reduction in cigarettes smoked per day from 12 to 6 cigarettes (average cigarette consumption based on population samples (e.g. [71]) and a 30% reduction in CO levels (from 18.5 to 13 parts per million (ppm); baseline estimate based on a opportunistically recruited population sample [72]).

Based on latest figures, it is estimated that involvement of two sites per Trust would reach around 100 patients per month per Trust. With smoking prevalence higher in this than in the general population, at around 40%, and with a conservative estimate of a consenting rate of around 15%, we therefore anticipate around six participants per Trust per month to be included in the feasibility trial, resulting in a total recruitment time of four months, with an additional month added as a buffer to account for uncertainty around the recruitment rate.

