The acceptability of the intervention and research procedures will be investigated using a short proforma based on the Theoretical Framework of Intervention Acceptability [63], provided to all participants at follow-up. This will be complemented by qualitative interviews conducted with a sample of approximately 18 participants from the intervention and control group (including, wherever possible, those who disengaged during the course of the study). We will gain insights into patients' experience with the intervention and barriers to and facilitators of success, both in terms of the intervention content and the research process. MHR (or CPN) delivering the intervention in each Trust will provide detailed feedback on their experience, and on barriers and facilitators to

delivery, through feedback diaries and interviews; in addition, in-depth qualitative interviews will be conducted with six MHR/CPNs (two from each Trust).

The attrition rate will be measured as the number of participants who fail to complete follow-up at 1 month. In order to ensure a sufficiently robust effect estimate, which can be affected by high attrition rates in intention to treat analyses [64], attrition rates should not exceed 30%, typical for smoking cessation trials in this population [65] (see 3.14). Reasons for withdrawal will be obtained, where possible. In addition, adherence to treatment (e-cigarette use) will be assessed at 1-month follow up.

3.8.2.2 Clinical (smoking-related) outcomes: This is the primary clinical outcome measure for the feasibility trial, assessed at 1-month follow up. Continuous abstinence will be defined as not having smoked in the two weeks prior to follow-up (weeks 5 and 6 from enrolment), verified by a CO reading below 10 ppm, in keeping with the standard measure used in Stop Smoking Services. This measure will be used to determine whether to progress to Phase II and a full trial, based on the confidence interval approach (see 3.9 and 3.14).

3.8.3 Secondary outcome measures:

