3.10 Analyses

The results of the feasibility trial (e.g., preliminary effectiveness, feasibility and acceptability) will determine whether a full RCT (Phase II) is viable. The primary outcome, smoking abstinence for weeks 2-4 from enrolment or target quit date (for those who set a date within one week of enrolment), assessed at 1-month follow-up will be descriptively analysed in line with the one-sided confidence interval approach [47]. Consenting rate, recruitment frequency as well as attrition and adherence rate will be calculated to determine feasibility and to decide which recruitment route is most effective. Qualitative data on acceptability will be analysed using Framework analysis, guided by the Theoretical Framework of Intervention Acceptability [63], to determine themes related to barriers and facilitators to intervention acceptability, and with thematic analysis [73] to explore interview data from trial participants and research and CMHT or allied mental health professional staff. We will also conduct a simple cost effectiveness analysis to determine incremental cost-effectiveness ratios for each additional quitter in the intervention compared with control group. Secondary clinical outcome measures will be analysed using generalised linear models (with intervention allocation specified as between-group factor and time as within-group factor) to determine reductions in cigarette consumption and exhaled breath carbon-monoxide readings and changes in mental health measures from baseline to 1-month follow-up. Fidelity will be determined using an established methodology of BCT-coded audio recording of intervention sessions [66]. Finally, for all quantitative analyses (primary and secondary outcome measures), Bayes Factors will be calculated to examine for non-significant results whether the associations indicated evidence of no effect or data being insensitive to detect an effect, and for significant results, the strength of evidence [74].

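### The 80% power that section 3.9 claims for smoking reduction is calculated for 18 expected reducers, so it is not established for the planned analysis of all participants

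*Protocol*

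**What the plan says.** Section 3.9 sets the size of Phase I: "The target sample size for the randomised controlled feasibility trial will be 72, with 36 participants allocated to each group". After arguing for that number from the abstinence outcome by the confidence interval approach, it adds a second claim: "the Phase I study is powered to detect clinically relevant within-subject changes in two secondary clinical outcome measures: cigarette and exhaled breath CO reductions". The support given is "Half the sample size in the intervention group (those expected to reduce consumption, n=18) provides 80% power to detect a medium- to large-sized effect". The effect size is tied to two changes. One is "Cohen's d=0.7), reflecting a 50% reduction in cigarettes smoked per day from 12 to 6 cigarettes", and the other is "a 30% reduction in CO levels (from 18.5 to 13 parts per million (ppm". The same paragraph makes a fall of at least half in cigarettes (or 30% in CO) the target outcome.

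The analysis is described elsewhere. Section 3.8.3.2 computes the change in cigarettes and CO in both arms. Section 3.10 analyses the secondary clinical outcomes with "generalised linear models (with intervention allocation specified as between-group factor and time as within-group factor"). On losses, section 3.8.2.1 says that "attrition rates should not exceed 30%, typical for smoking cessation trials in this population". Section 3.13 repeats that limit as a progression criterion.

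**The concern.** A power statement is useful only if it describes the analysis that will be done. Here the calculation takes half of the intervention arm, namely those expected to reach the reduction target, and gives them the full effect. The other half, whose change is expected to be smaller, are left out of both the sample size and the effect. The analysis includes them. It also includes the controls, and it will be run after some loss to follow-up that section 3.9 does not allow for.

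At stake is how the reduction results will be read. A reader told that the study is powered for them may give a non-significant whole-arm change more weight than the design supports.

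**Working it through.** **Inputs from the protocol.** 36 per arm, 18 expected reducers, d=0.7, cigarettes 12 to 6, CO 18.5 to 13 ppm (all section 3.9); attrition up to 30% (section 3.8.2.1).

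**Assumptions made here.**
- Two-sided alpha of 0.05. Section 3.9 gives none for this claim; section 4.6 gives this value for Phase II.
- The change in non-reducers, which the protocol does not state. A range is used.
- Expected reducers fall by 6 cigarettes on average.

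**1. The plan's own figure.** Paired t-test, noncentral t with 17 degrees of freedom and noncentrality 0.7 × √18 = 2.97: power is 79.9%. The stated 80% is reproduced. With 30% loss, 18 × 0.7 = 12.6 people remain. Power is 59.9% with 12 and 64.0% with 13.

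**2. Implied SD of change.** Cigarettes: 6/0.7 = 8.57. CO: (18.5 − 13)/0.7 = 7.86 ppm. The protocol states neither.

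**3. Whole intervention arm.** Half fall by 6 on average and half by x, each with SD 8.57.
- Mean change = (6 + x)/2
- SD = √(8.57² + ((6 − x)/2)²)
- d = mean/SD, used in a paired t-test with n = 36, or with n = 25 (36 × 0.7 = 25.2)

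| x (cigarettes) | Mean | SD | d | Power, n=36 | Power, n=25 |
|---|---|---|---|---|---|
| 0 | 3.00 | 9.08 | 0.33 | 49% | 35% |
| 1.5 | 3.75 | 8.86 | 0.42 | 69% | 53% |
| 2.5 | 4.25 | 8.75 | 0.49 | 81% | 64% |
| 3 | 4.50 | 8.70 | 0.52 | 85% | 70% |

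If d=0.7 held for the whole arm, power would be 98% with 36 and 92% with 25. The calculation depends only on standardised effects, so the same percentages apply to CO when non-reducers change by the same fraction of the reducers' fall.

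**4. Arm-by-time comparison.** Controls are assumed unchanged, with SD 8.57. With x = 0, 1.5 and 3, the two-sample t-test on change has about 30, 44 and 59% power at 36 per arm, and 22, 32 and 44% at 25 per arm.

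**5. Precision at SD 8.57.** The 95% CI half-width is t × 8.57/√n within an arm and t × 8.57 × √(2/n) between arms.
- n=36: 2.03 × 8.57/6 = 2.9, and 1.994 × 8.57 × √(2/36) = 4.0 cigarettes
- n=25: 2.064 × 8.57/5 = 3.5, and 2.011 × 8.57 × √(2/25) = 4.9 cigarettes

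**The case against.** **The shortfall depends on an unstated quantity.** This stands. With full follow-up, within-arm power passes 80% once non-reducers fall by about 2.5 cigarettes. It would also rise if reducers fell by more than 6 on average, which the target of at least half allows. Section 1 cites a UK pilot with a fall of 50% or more in average consumption. If that is a whole-sample average, d=0.7 could apply to the entire arm. So the documents do not show that the planned analysis lacks 80% power, only that the protocol has not shown that it has it.

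**Taking 18 of 36 is a crude discount for non-responders.** Possibly, but it discounts only the sample size. Allowing for non-responders would keep all 36 and shrink the average effect.

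**A reader might infer a circular test, in people selected because they reduced.** The documents do not support that. The 18 are a planning assumption, and no reducer-only analysis is planned.

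**The between-arm figures refute nothing.** Correct. The claim covers within-subject change only. Those figures show how far it is from the model in section 3.10.

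**Misreading of a null result is already guarded against.** In part. Section 3.10 plans Bayes Factors for all quantitative analyses, to separate evidence of no effect from insensitive data. That helps interpretation afterwards but does not make the design statement true. Likewise, 30% is a ceiling on attrition and not a forecast, so the figures for 25 completers are the lower end of what the protocol tolerates.

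**Conclusion.** The statement is wrong as written, because the population behind the power figure is not the population to be analysed. It is not an arithmetic error. For the whole intervention arm, within-subject power is about 49 to 85% with full follow-up and about 35 to 70% with 25 completers. This rests on two-sided alpha of 0.05, half the arm changing by d=0.7, SD of change 8.6 within each half, and non-reducers falling by 0 to 3 cigarettes. On that premise, with 25 completers power stays below 80% across the range. With all 36 it reaches 80% only towards the upper end.

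The consequence is modest. Cigarette and CO reduction are secondary outcomes and are not listed among the stop/go criteria in section 3.13, and n=72 is argued separately from abstinence. The finding gives no ground for a larger Phase I.

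**What to change.** In section 3.9, withdraw the sentence claiming 80% power for cigarette and CO reduction. Alternatively, restate it for all intervention participants, with the assumed change in non-reducers, the SD of change and the attrition allowance written out.

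In either case, add the expected precision for the whole arms. With an assumed SD of change of 8.6 cigarettes, the 95% CI half-width is about 2.9 within an arm and 4.0 between arms at 36 per arm, and about 3.5 and 4.9 at 25 per arm. Say that this SD is back-calculated from d=0.7, and that the SD over a mixed arm may be somewhat larger (9.08 if non-reducers do not change, which widens the within-arm figure at n=36 to about 3.1). For CO, multiply the half-widths by 7.86/8.57 = 0.92 to obtain ppm.

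Keep the models and Bayes Factors of section 3.10 in all randomised participants. The cost is a few sentences. Sample size, outcomes and procedures do not change, but the stated property becomes less favourable.
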